Likewise, 5 subjects with advanced pancreatic cancer were treated with synthetic RAS peptides used as a cancer vaccine. All subjects were vaccinated at Day 0, and booster vaccinations were performed similarly on Days 7-10 and at 1 month. Further booster vaccinations were performed at 4-6-week intervals or as long as the subject's immunological response and overall performance status permitted over a period of 2 to 10 months. The treatment was well tolerated and could be repeated multiple times in the same subject. No sign of toxicity and no adverse events (AEs) were observed [Gjertsen et al, 1996].

ELI-002 is expected to elicit common side effects often associated with vaccines such as local skin reaction, fever, fatigue, pain, among others which generally subside within a day or two. Reactogenicity refers to a subset of reactions that occur soon after vaccination and are a physical manifestation of the inflammatory response to vaccination. In clinical trials, information on expected signs and symptoms after vaccination is actively sought (or 'solicited'). These symptoms may include pain, redness, swelling or induration for injected vaccines, and systemic symptoms, such as fever, myalgia, headache, or rash. The broader term "safety" profile refers to all AEs that could potentially be caused/triggered or worsened at any time after vaccination, and includes AEs, such as anaphylactic reactions, diseases diagnosed after vaccination and autoimmune events.

The administration of 48 µg Peptide with either 5 or 25 µg Adjuvant was well tolerated in the rodent Study No. 2795-002 with a dose-dependent reduced incidence and severity of local irritation and limited associated effects. Therefore, the NOAEL was 48 µg Amph-Peptides/25 µg Adjuvant. Local reactions were considered adverse at the high adjuvant Amph-CpG-7909 dose in the GLP toxicity study which confirms the importance of reactogenicity monitoring. Local

reactions and some flu-like symptoms are expected in subjects who receive peptide injections, and there is always a possibility of hypersensitivity reactions. Injection site reaction is the only AE known to be attributed to ELI-002. Reactogenicity monitoring will occur throughout the ELI-002-001 trial (see [Section 12.2.1.3](#))

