## **6.7. Management of Study Drug-Related Events**

### **6.7.1. Temporarily Suspending Treatment Administration**

If a subject meets any of the following conditions within 48 hours prior to the scheduled administration of the trial treatment, treatment administration will be temporarily suspended:

1. To reduce the risk of CRS, subjects will not be given a repeat dose of ELI-002 if they are exhibiting  $T \geq 38^{\circ}\text{C}$  and/or  $\text{IL-6} \geq 500 \text{ pg/mL}$  (cytokine collection, including IL-6, may be performed up to 7 days prior to treatment). In addition, if a subject exhibits  $\text{IFN}\gamma \geq 1000 \text{ pg/mL}$ , the Elicio medical monitor should be contacted for consultation.
2. Adverse event(s) that meet the definition of DLT caused by prior treatment. See [Section 6.7.3](#) for the definition of a DLT; see [Section 12.4](#) for the definition of Common Terminology Criteria for Adverse Events (CTCAEs).
3. Any subsequent dosing in a subject who has experienced Grade  $\geq 2$  CRS/ immune effector cell-associated neurotoxicity syndrome (ICANS)

Investigators must consult the medical monitor to discuss any subjects meeting the above criteria.

In the event the ELI-002 dose is held, the subject should not receive any make up dose and remain on the original protocol schedule (ie, their next dose will be at the next protocol-specified dose if they meet the criteria for dosing). All trial procedures and treatment administration will be resumed as soon as the subject's condition allows or at the investigator's discretion after Sponsor approval.

The trial may proceed at a lower dose, at a less frequent schedule, or omitting the Amph-CpG-7909 adjuvant while continuing to administer the Amph-Peptides, based on emerging toxicity or pharmacodynamic data until the MTD is determined.

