### 6.7.3. Dose-limiting Toxicity Guidelines

A DLT will be defined as any event at least possibly related to ELI-002 as follows:

- a. Any Grade  $\geq 3$  non-hematologic toxicity except asymptomatic laboratory abnormalities (see Section 12.2.1.1)
- b. Any Grade  $\geq 3$  toxicity involving major organ systems for greater than 72 hours and occurring within 28 days of subcutaneous administration
- c. Grade 3 CRS that does not resolve to  $\leq$  Grade 2 within 7 days
- d. Any Grade 4 CRS that does not improve to  $<$  Grade 2 within 72 hours
- e. Any Grade  $\geq 3$  autoimmune disorder
- f. Any Grade  $\geq 3$  rash that does not resolve to  $\leq$  Grade 1 within 7 days with appropriate treatment

The DLT observation period will be 28 days.

Maximum tolerated dose definition: The MTD is defined as the highest dose level with a DLT incidence  $<33\%$  of cohort subjects.

See protocol Section 6.7.1 and Section 6.8 for management of toxicity.

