#### 6.8.5. Management of Maculo-Papular or Acneiform Rashes, Injection Site Reactions

For routine injection site reactions manifested as maculo-papular or acneiform rashes, erythema, induration, pruritis and pain, topical application of cool compresses, antihistamine or corticosteroids may be used. If needed, systemic antihistamines and antipyretics may be added.

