#### **12.2.1.3. Reactogenicity to the Vaccine**

Injection site reactions, skin rash, and pruritis will not be considered a DLT or safety event and should be recorded in the patient diary and eCRF for reactogenicity. (See [Section 6.7.3](#) for DLT

Guidelines, [Section 6.8.5](#) for toxicity management, and [Section 12.2.1.2](#) for SAE definition.) Severe skin rashes such as Steven-Johnson Syndrome or toxic epidermal necrolysis (TEN) will be considered a DLT and should be reported on the eCRF as safety events including SAE as appropriate. Reactogenicity monitoring will include subject's reactogenicity to the trial drug (vaccine). This will be captured at several time points as follows:

- 1-hour post ELI-002 dose administration (subjects will be observed in the clinic for at least 1-hour after each dose)
- 1-week post ELI-002 dose administration (subjects will record daily observations in diary)
- Any unresolved reactogenicity event should be followed until resolution.

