## 12.5. Recording Adverse Events

Adverse events spontaneously reported by the subject and/or in response to an open question from the trial personnel or revealed by observation will be recorded during the trial at the investigational trial center. Treatment emergent AEs (TEAEs) are defined as events not present prior to the initiation of study drug or any event already present that worsens in either intensity or frequency following exposure to study treatment. AEs must be recorded in the eCRF and on forms as provided by Elicio. The AE term should be reported in standard medical terminology when possible. For each AE, the investigator will evaluate and report the onset (date and time), resolution (date and time), severity, causality, action taken, outcome, and whether or not it caused the subject to discontinue the trial.

Severity will be assessed according to CTCAE or ASTCT as appropriate for the event. For AEs not described in the consensus criteria, the following scale will be used:

- Mild (awareness of sign or symptom, but easily tolerated. Concomitant prescription medications are not ordinarily needed for relief of symptoms)
- Moderate (discomfort sufficient to cause interference with normal activities. Concomitant prescription medications/treatment(s) may be needed for relief of symptoms)
- Severe (incapacitating, with inability to perform normal activities. Requires interruption or discontinuation of study medication. Systemic drug therapy or other treatment is needed)

Reactogenicity will be assessed according to the toxicity grading scale for local reactions for preventive vaccines (see [Section 12.2.1.3](#)).

It is important to distinguish between serious and severe AEs. Severity is a measure of intensity whereas seriousness is defined by the criteria under [Section 12.2.1.2](#). An AE of severe intensity may not be considered serious.

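### Protocol 12.2.1.3 and the DLT definition in Protocol 6.7.3 / SAP 8.1 classify a related Grade ≥3 injection-site reaction or pruritis differently, and no text says which rule prevails

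*Protocol*

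**What the plan says.** - Protocol 12.2.1.3: "Injection site reactions, skin rash, and pruritis will not be considered a DLT or safety event". These events go to the patient diary and the reactogenicity eCRF. No grade is mentioned. The one exception is that "Severe skin rashes such as Steven-Johnson Syndrome or toxic epidermal necrolysis (TEN) will be considered a DLT"; those rashes are to be reported as safety events. The section cross-refers to 6.7.3, 6.8.5 and the SAE definition.
- Protocol 6.7.3(a), with the same text in the synopsis and SAP 8.1: a DLT is any at least possibly related Grade ≥3 "non-hematologic toxicity except asymptomatic laboratory abnormalities". Criterion (f) counts a Grade ≥3 rash only if it fails to settle to at most "Grade 1 within 7 days with appropriate treatment".
- SAP 13.7.1: a footnote gives Protocol 6.7.3 as the DLT definition and does not mention 12.2.1.3. An optional DLT flag is placed on adverse event listings. Reactogenicity has its own listing and a summary by type and toxicity grade.
- Protocol 6.7.1: dosing is suspended for "Adverse event(s) that meet the definition of DLT caused by prior treatment".
- Protocol 12.5: "Reactogenicity will be assessed according to the toxicity grading scale for local reactions for preventive vaccines". It cites 12.2.1.3 for that scale, but 12.2.1.3 contains none. Other AEs are graded by CTCAE v5, and CRS and ICANS by ASTCT.
- Protocol 6.8.5, on management, opens "For routine injection site reactions manifested as maculo-papular or acneiform rashes".

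**The concern.** MTD and RP2D form a primary endpoint and rest on the DLT count. Two sections of the protocol give different answers on whether a severe local reaction enters that count, and the SAP adopts only one of them.

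The event type matters here. Protocol 4.6.3 says "Injection site reaction is the only AE known to be attributed to ELI-002", and Protocol 4.4.1.2 attributes the mouse toxicity mainly to the adjuvant, the component being escalated. The SAP adds cohorts at 5.0 and 10.0 mg, which are 5.0/2.5 = 2 and 10.0/2.5 = 4 times the highest dose planned in the protocol.

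The conflict also reaches individual subjects. A Grade 3 injection-site reaction leads to a dose hold under 6.7.1 if 6.7.3(a) governs. If 12.2.1.3 governs, the DLT item of 6.7.1 does not apply.

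There is a second-order question about data flow. Events sent to the reactogenicity eCRF, graded on another scale, may not reach DLT outputs built from AE records.

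**Working it through.** **1. The plan's own rule is internally consistent.** 1/6 = 16.7%, below the 33% MTD limit. 2/6 = 33.3%, not below it. So the rule that 2 or more of 6 is toxic agrees with the MTD definition. The difficulty is what goes into the numerator.

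**2. The two rules side by side**, for an at least possibly related event in the 28-day window:

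| Event | Protocol 12.2.1.3 | Protocol 6.7.3 / SAP 8.1 | Result |
|---|---|---|---|
| Injection-site reaction, Grade ≥3 | Not a DLT; no exception given | DLT under (a) | Unresolved |
| Pruritis, Grade ≥3 | Not a DLT; no exception given | DLT under (a) | Unresolved |
| Rash, Grade ≥3, not settled in 7 days | Excluded unless it falls under the severe-rash exception, which is worded by example | DLT under (f) | Partial conflict |
| Rash, Grade ≥3, settled in 7 days | As above | Not under (f); yes under a literal (a) | Unclear within 6.7.3 itself |
| Any of these, Grade 1–2 | Not a DLT | Not a DLT | Agree |

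**3. Effect on the count**, where the only candidate events are related Grade 3 injection-site reactions:

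- One subject in 3: 1/3 (enrol three more) against 0/3 (escalate).
- Two in 3: 2/3 (toxic dose) against 0/3.
- Two in 6: 2/6 (toxic dose) against 0/6.

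**4. How often the readings could part.** The documents give no Grade ≥3 rate, so r per subject is an assumption. With q = 1 − r and no other DLTs:

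- P(counts differ in the first 3) = 1 − q³.
- P(toxic if counted) = 1 − [q³ + 3rq² × q³]. The bracket is the chance of 0/3, or of 1/3 followed by 0/3.
- P(toxic if excluded) = 0.

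| Assumed r | Counts differ in first 3 | Toxic if counted | Toxic if excluded |
|---|---|---|---|
| 5% | 0.143 | 0.027 | 0 |
| 10% | 0.271 | 0.094 | 0 |
| 20% | 0.488 | 0.291 | 0 |
| 33% | 0.699 | 0.566 | 0 |

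Example at r = 10%: q³ = 0.729 and 3rq² = 0.243, so 0.729 + 0.243 × 0.729 = 0.906 and 1 − 0.906 = 0.094.

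Now add an independent 10% rate of other DLTs. The probability of escalating is 0.906 with these events excluded. With them counted it is 0.824, 0.730 and 0.536 at r = 5%, 10% and 20%. These figures describe the count rule only; the Safety Monitoring Committee (SMC) may decide otherwise.

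**5. Route of the data.** Protocol 12.2.1.3 contrasts recording for reactogenicity with reporting as a safety event. SAP 13.7.1 lists DLTs among the by-subject listings of AE data and gives reactogenicity a separate listing with no DLT flag. It does not say whether the DLT derivation reads the reactogenicity form, or which scale defines Grade 3 for these events.

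**The case against.** The strongest reply is that 12.2.1.3 is a specific rule overriding a general one. It has real support. Criterion (a) cannot be applied literally beside its own list: it would make a DLT of Grade 3 CRS that resolves within 7 days, Grade 4 CRS that improves within 72 hours, and Grade ≥3 rash that settles within 7 days. Criteria (c), (d) and (f) would then have no effect. So (a) already needs to be qualified by narrower provisions, and 12.2.1.3 is the only provision on the DLT status of injection-site reactions. Protocol 4.6.3 also separates expected reactogenicity from the wider safety profile, so the exclusion may be deliberate. This reading is coherent, and for that reason the conflict should not be called a flat contradiction. But no text adopts it. Section 6.8.4 points the other way: it treats (a) as a catch-all that takes in autoimmune events already named in (e). If the override is intended, SAP 8.1 and 13.7.1 state the wrong definition.

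A second reply is that 12.2.1.3 means only the routine reactions of 6.8.5. That is sensible but unwritten. A reader might equally infer that the protocol excludes reactions of every grade by design. The section is silent on grade, so that too is an inference.

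Third, there are safeguards. The SMC reviews physical findings and all available safety data, the investigator may stop treatment for an intolerable AE, the medical monitor must agree before boosters resume after toxicity, unresolved reactions are followed, and reactogenicity is tabulated by grade. These reduce the risk to subjects and make Grade 3 reactions visible. They do not settle whether such a reaction is a DLT.

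**Conclusion.** The concern holds as an unresolved conflict between stated rules. A related Grade ≥3 injection-site reaction or pruritis in the 28-day window has two possible DLT classifications, and for rash the conflict is partial. This can move a cohort from 0/6 to 2/6, and so from escalation to a toxic dose, and it can change whether 6.7.1 requires a dose hold. The probabilities above rest on assumed rates, independence between subjects and mechanical use of the count rule. They are not evidence about what happened in this trial.

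Two stronger conclusions may tempt a reader, and the documents support neither. One is that Grade 3 local reactions were in fact left out of the DLT count. SAP 13.7.1 does point to 6.7.3, and neither the eCRF nor the SMC Charter was provided; either might settle the matter. The other is that escalation decisions or the MTD were wrong. No event data are given, and the SMC was not bound to the count alone.

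The protocol synopsis gives last enrolment as 2Q2023 and SAP Version 3.0 is dated August 2024, so escalation is probably complete. What remains is mainly the reported DLT counts and the stated basis for the MTD and RP2D. This should be fixed before final reporting. It does not in itself invalidate the trial.

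**What to change.** 1. State in Protocol 12.2.1.3 and in SAP 8.1 and 13.7.1 which rule governs Grade ≥3 injection-site reactions and pruritis. The safer choice, consistent with 6.7.3 and 6.8.5, is to limit the exclusion to Grade 1–2. If the sponsor intends the full exclusion, write it into 6.7.3 and the SAP definition instead.
2. Name the grading scale that decides DLT status for these events.
3. In SAP 13.7.1, derive DLTs from both the AE and the reactogenicity eCRFs.
4. For completed cohorts, tabulate DLT counts per cohort under both readings, and have the SMC re-review the MTD/RP2D basis if they differ.

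Cost: a sentence in the protocol, matching wording and a derivation rule in the SAP, and one small table. If no Grade ≥3 event of this kind occurred in the window, the table shows that and the matter closes. The downside is that a cohort's reported DLT count may rise and need SMC re-review.

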#### **12.2.1.4. Cytokine Release Syndrome**

The definition, management, and grading of CRS are provided in [Section 6.8](#).

### **12.3. Relationship to Trial Drug**

An investigator who is qualified in medicine must make the determination of relationship to the investigational product for each AE (Unrelated, Possibly Related, or Related). The investigator should decide whether, in his or her medical judgement, there is a reasonable possibility that the event may have been caused by the investigational product.

Unrelated: The AE is definitely not associated with the study drug administration and is judged related to causes other than the study drug.

Possibly Related (Suspected Adverse Reaction [SAR]): A causal relationship between treatment with the study drug and the AE is at least a reasonable possibility, ie, the relationship cannot be ruled out. This implies a lesser degree of certainty about causality than a related AE. Additional evidence to suggest a SAR includes:

- Occurrence of uncommon AEs that are known to be strongly associated with drug exposure (eg, anaphylaxis, angioedema, blood dyscrasias, rhabdomyolysis, hepatic injury, Stevens-Johnson Syndrome)
- Occurrence of AEs that are uncommon in the study population, but not commonly associated with drug exposure (eg, intussusception in healthy infants)

Related (Adverse Reaction): A causal relationship between the study drug administration and the AE is definite.

If the relationship between the AE/SAE and the investigational product is determined to be "possible" the event will be considered related to the investigational product for the purposes of expedited regulatory reporting.

## 12.4. Severity of Adverse Events

The CTCAE Version 5 displays Grades 1 through 5 with unique clinical descriptions of severity for each AE based on this general guideline:

- **Grade 1** Mild; asymptomatic or mild symptoms; clinical or diagnostic observations only; intervention not indicated
- **Grade 2** Moderate; minimal, local or noninvasive intervention indicated; limiting age appropriate instrumental activities of daily living (such as preparing meals, shopping for groceries or clothes, using the telephone, managing money, etc.)
- **Grade 3** Severe or medically significant but not immediately life-threatening; hospitalization or prolongation of hospitalization indicated; disabling; limiting self-care activities of daily living (such as bathing, dressing and undressing, feeding self, using the toilet, taking medications, and not bedridden)
- **Grade 4** Life-threatening consequences; urgent intervention indicated
- **Grade 5** Death related to AE.

For CRS/ICANs, AEs will be graded according to the ASTCT criteria ([Table 18](#) and [Table 21](#)).

## 12.5. Recording Adverse Events

Adverse events spontaneously reported by the subject and/or in response to an open question from the trial personnel or revealed by observation will be recorded during the trial at the investigational trial center. Treatment emergent AEs (TEAEs) are defined as events not present prior to the initiation of study drug or any event already present that worsens in either intensity or frequency following exposure to study treatment. AEs must be recorded in the eCRF and on forms as provided by Elicio. The AE term should be reported in standard medical terminology when possible. For each AE, the investigator will evaluate and report the onset (date and time), resolution (date and time), severity, causality, action taken, outcome, and whether or not it caused the subject to discontinue the trial.

Severity will be assessed according to CTCAE or ASTCT as appropriate for the event. For AEs not described in the consensus criteria, the following scale will be used:

- Mild (awareness of sign or symptom, but easily tolerated. Concomitant prescription medications are not ordinarily needed for relief of symptoms)
- Moderate (discomfort sufficient to cause interference with normal activities. Concomitant prescription medications/treatment(s) may be needed for relief of symptoms)
- Severe (incapacitating, with inability to perform normal activities. Requires interruption or discontinuation of study medication. Systemic drug therapy or other treatment is needed)

Reactogenicity will be assessed according to the toxicity grading scale for local reactions for preventive vaccines (see [Section 12.2.1.3](#)).

It is important to distinguish between serious and severe AEs. Severity is a measure of intensity whereas seriousness is defined by the criteria under [Section 12.2.1.2](#). An AE of severe intensity may not be considered serious.

## 12.6. Pregnancy

Should a pregnancy occur within 30 days of the last ELI-002 dose in a female subject, or in the partner of a male subject, it must be reported on Elicio's paper pregnancy form. Neither pregnancy itself nor an induced elective abortion to terminate a pregnancy for non-medical reasons is considered an AE. However, an induced therapeutic abortion to terminate a pregnancy due to complications or other medical reasons will be recorded as an SAE. The underlying medical reason for this procedure should be recorded as the AE term. Pregnancy outcomes considered to be SAEs are:

- Spontaneous abortion (miscarriage)
- Stillbirth
- Induced therapeutic abortion to terminate pregnancy due to complications or other medical reasons
- Neonatal death; this includes all neonatal deaths that occur within 1 month of the expected birthdate (ie, either before or after the expected birth date)
- Infant death occurring 1 month after birth, if the investigator assesses the death as possibly related to in utero exposure to study treatment
- Congenital anomaly (in live birth or aborted fetus)

If the subject has signed the pregnancy informed consent, the outcome of all pregnancies (spontaneous miscarriage, elective termination, normal birth or congenital abnormality) must be followed up and documented even if the subject was discontinued from the trial.

## 12.7. Reporting Adverse Events

All AEs and SAEs will be reported on the appropriate eCRF pages, which will also be the reporting mechanism to Elicio safety/pharmacovigilance. All AEs (related and unrelated) will be recorded from first dose administration until 30 days after the end of study treatment administration. All SAEs (related and unrelated) will be recorded from the signing of the ICF until 30 days after the end of study treatment administration. All SAEs must be reported to Elicio or their designee within 1 business day of the first awareness of the event. The investigator must verify the accuracy of the information recorded on the SAE pages with the corresponding source documents.

Additional follow-up information, if required or available, should all be sent to Elicio or its designee within one business day of receipt and this should be completed on a follow-up SAE form, as well as documented with the original SAE source information and kept with the appropriate section of the subject source records.

Elicio is responsible for notifying the relevant regulatory authorities of certain events. It is the PI's responsibility to notify the Institutional Review Board (IRB) of all SAEs that occur at his or

her trial center in accordance with local IRB requirements. Investigators will also be notified of all unexpected, serious, drug-related events (Suspected Unexpected Serious Adverse Reaction [SUSAR] Reports) that occur during the clinical trial. Each trial center is responsible for notifying its IRB of these additional SAEs in accordance with local requirements. If the clinical site submits to a central IRB, SUSAR reports will be submitted by Elicio or its designee.

